Among the main causes of lack of control are the therapeutic inertia of the doctor, effect of the "white coat" and especially the lack of adherence of patients to the correct use of medication and healthy habits of life, especially to the restricted sodium diet and physical activity. Factors that contribute to a low adtake are multiple and at various levels. Barriers to treatment are barriers to the patient (multiple comorbidities, low level of knowledge of the disease, economic restrictions, lack of involvement in the decision-making process of the treatment) - in relation to the doctor (prescription of complex treatment regimens, communication barriers, lack of adequate information of adverse reactions, clinical inertia), and in relation to the health system (limitation of the time of medical consultations, limited access to care, lack of multiprofessional approach and health information technology) [5].

Non-adhering to antihypertensive drugs is highly prevalent in patients with uncontrolled hypertension [6,7]. It is estimated that between 50% and 80% of hypertensive patients receiving

prescription medication demonstrate suboptimal therapeutic adherence [8]. Other studies have shown that a quarter of patients who start newly diagnosed antihypertensive therapy fail to follow the initial prescription [9,10]. During the first year of treatment, most patients take the prescribed antihypertensive medication only 50% of the time, and only 1 in 5 patients have sufficient support to achieve the benefits observed in clinical trials (approximate 80% adherence) [11].

This relatively high proportion of non-adhering is due, at least partially, to the large number of pills to be taken, complexity of doses, presence of adverse reactions with multiple medication regimen, and the little insistence of physicians regarding better support when patients are consistently non-adherent [12].

However, the tendency to improve BP control rates (<140/90 mm Hg) among those on antihypertensive treatment to more than 70% suggests that recent strategies to improve hypertension and care with antihypertensive medication have been successful [13].

In relation to healthy lifestyle habits, adhering to a more restricted sodium diet is one of the most difficult to achieve, despite several efforts to reduce sodium intake in the population. Two-thirds of the salt consumption by the Brazilian population comes from the salt added directly to the meal. The numbers show that Brazilians consume more than twice – almost 12 grams (g) – of the amount recommended by the World Health Organization (WHO) [4]. Data from the Ministry of Health reveal that 90% of men and 70% of women consume more salt than the maximum recommended, 85.1% of adult Brazilians consider their salt consumption adequate [4]. Another important point between life habits is sedentary lifestyle, which can also contribute to the lack of adequate control of BP. There is much evidence that shows the benefit of physical activity to reduce BP, including providing the number of medications needed for control [3].

Therefore, it is essential to help patients adopt healthy measures to assist in the daily control of BP. As the barriers to therapeutic adherence are complex and varied, solutions to improve adherence at the population level should be multifactorial [14,15].

Several systematic reviews and meta-analyses have evaluated the impact of interventions on patients' adhering to antihypertensive medications and their benefits [16, 17].

Most interventions to improve the quality of AH care, medication and healthy habits and BP control are care based on a multidisciplinary team [18]. Different patient-centered models

with a multidisciplinary team showed an increase in the proportion of individuals with better blood pressure support and greater BP control [18,19,20,21,22].

One of the best and most effective models includes decision support systems (treatment algorithms), collaboration between team and patient, medication adherence, home BP monitoring, and patient self-care [23,24].

Recently, support systems such as electronic health records, remote monitoring based on new technologies and self-care support tools, can increase and intensify efforts based on the multidisciplinary team approach [25,26,27,28].

In this sense, some studies are being conducted on the use of mobile technology to control hypertension, aiming at greater access to the patient, education and awareness of the disease, as well as the patient's engagement in their care [29,30,31,32,33]. In a previously developed study, it was seen that virtual distance or face-to-face teaching, through "e-learning", helps to reduce the effect of the white coat and the anxiety of hypertensive patients, with an improvement in adherence to treatment [34].

However, it is not yet known the best technological tools to help hypertensive patients to improve treatment adhering to healthy life habits and, and consequently avoid the complications of AH. In addition, this tool needs to be feasible to be used by patients or caregivers, regardless of social class, preserving their intimacy, privacy and still obtaining the desired health improvement results.

Based on these arguments, the hypothesis of the proposal is that the use of an application developed by artificial intelligence adapted to individual needs and customs can help improve therapeutic adherence and provide better BP control in patients with uncontrolled hypertension.

2. Primary objective

To evaluate the effectiveness of an artificial intelligence application developed for home monitoring compared to institutional standard follow-up in patients with uncontrolled hypertension in the following parameters:

- a) To obtain adequate control of blood pressure (< 140/90 mmHg) of the office and of the blood pressure ambulatory monitoring (< 135/85 mmHg at wakefulness)
- b) Improving adherence to drug treatment assessed by a validated questionnaire

- c) Reduce dietary sodium intake and 24-hour urinary sodium
- d) Increase the performance of physical activity evaluated by number of daily steps
- e) Reduction of body weight and abdominal circumference

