3.1. Study design

Randomized study with patients with uncontrolled hypertension followed at the Outpatient Clinic of the Hypertension Unit of the Heart Institute (InCor-HCFMUSP), for the use of an application for monitoring and engagement to antihypertensive treatment - compared to the standard follow-up of the institution in a 12-month follow-up.

The study involves the direct participation of an institutional multidisciplinary team with an international partnership and a national institution of advanced technology in artificial intelligence. The hospital's team includes physicians, nurses, nutritionists, psychologists, physical educators and biomedical, supported by the institution's own innovation team. The international team includes all members of the Inavya Ventures LTd.

Will be included 100 patients diagnosed with primary arterial hypertension under drug treatment, with at least 3 classes of antihypertensive drugs in an optimized dose, aged 20 to 65 years, and who present clinic BP ≥ 140 and/or 90 mmHg, and wakefulness BP in ambulatory BP monitoring $\geq 135/85$ mmHg. Patients or their caregivers should also be able to use mobile phones and apps.

Patients with stroke sequelae or those with significant cognitive dysfunction will be excluded.

Randomization will be done in the 1:1 form using electronic randomization system, without knowledge by the team involved in the study. There will be two groups in the project,

so that, patients will be randomized to intervention group (application use) or control group (standard follow-up of the institution).

In the intervention group (N= 50), patients will receive a cellular device (by donation consigned by a telephone company) for the exclusive use of the application within 12 months. In this mobile device will be installed, with the guidance of the multidisciplinary team, the AVATR application developed in partnership with the company Inavya Ventures Ltd., where they will be digitized with individualized code for each patient, personal data, including age, gender, behavioral patterns and lifestyle habits (walks, type of diet, quality of sleep, etc.), and daily medications used.

The data will be allocated in a dedicated cloud and protected by cutting edge encryption. All this part of data capture and storage is in accordance with the rules of the General Data Protection Law (GDPL) as well as the General Data Protection Regulation (GDPR), the uk regulation.

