Patients will have a 15 days adaptation period to the use of the application, where they will receive virtual guidance by the multidisciplinary team for the correct use. After this period, patients will perform an evaluation by the medical and nursing staff, where clinical data (clinic blood pressure, weight, height and abdominal circumference) will be collected and patients will answer questionnaires on quality of life, anxiety, sleep quality, food intake and therapeutic adherence. In this same consultation, patients will receive an automatic blood pressure measurement device (described in the methods) to make household blood pressure measurement according to nursing guidance. Blood samples will also be collected for biochemical profile (total cholesterol and fractions, triglycerides, fasting glycemia, potassium, serum creatinine) and 24-hour urine sample for urinary sodium dosage, these tests will be collected at the Research Center and the analysis will be performed by the institute's laboratory.

The application automatically receives input data from each patient, such as BP MEASUREMENTS by the device and also the steps walked recorded by own in a third-party application also installed on the mobile phone. This data is safely transferred to the cloud server and analyzed based on an algorithm developed with the help of healthcare professionals to generate a customized lifestyle modification program designed for each patient. The application has automatic messages for the time of medication, in addition to strengthening nutritional guidance, physical activity and emotional order through automatic motivating phrases and also by access to educational videos. Another important tool is speech recognition that allows the patient to send data by voice system when there is difficulty in typing communication.

The multiprofessional team will receive alerts by email or the application platform, according to pre-established limits of blood pressure or symptoms, allowing immediate contact of the team for the necessary guidance. The multidisciplinary team will contact patients in the digital intervention group every 4 weeks for guidance based on the insertions made by patients in the application during the period. The correct use of medication as well as the adoption of healthy life habits will be reinforced in this contact.

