The control group (N= 50) will perform the same initial evaluation and answer the same questionnaires as described above for the intervention group. In this evaluation will receive guidance regarding the adoption of life habits by the multidisciplinary team. The control group will receive reinforcement of guidance only in clinic face-to-face visits.

The visits of the study after the patient's inclusion will take place every 12 weeks (Visits 2, 3, 4 and 5), totaling 4 visits after the initial visit, with the final visit after 12 months. Patients will perform 24-hour ambulatory blood pressure monitoring (ABPM) at visits 2, 3 and 5. In visits 2 to 5, the patient will have the measurement of blood pressure from the office, weight and abdominal circumference, and data on symptoms and events that occurred (hospitalizations, emergency room visits, symptoms) will be collected. In the last visit (12-month), in addition to these measures, the questionnaires performed on the first visit and laboratory dosages will be repeated.

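### Section 2 gives five parameters (eight measures) equal primary status with no success rule, and Section 3.12 states no between-arm test of blood pressure control

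*Protocol*

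**What the plan says.** Section 2 states one primary objective: the effectiveness of the app compared with the institution's standard follow-up on items (a) to (e).

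- (a) "To obtain adequate control of blood pressure (< 140/90 mmHg) of the office and of the blood pressure ambulatory monitoring", with an awake ambulatory threshold of 135/85 mmHg.
- (b) Adherence to drug treatment, by questionnaire.
- (c) "Reduce dietary sodium intake and 24-hour urinary sodium".
- (d) Number of daily steps.
- (e) "Reduction of body weight and abdominal circumference".

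Section 2.1 then gives a separate secondary tier.

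On timing, Section 3.1 says: "In visits 2 to 5, the patient will have the measurement of blood pressure from the office, weight and abdominal circumference". It also says: "Patients will perform 24-hour ambulatory blood pressure monitoring (ABPM) at visits 2, 3 and 5". For the rest: "In the last visit (12-month), in addition to these measures, the questionnaires performed on the first visit and laboratory dosages will be repeated". Steps appear only in the description of the app, which receives "the steps walked recorded by own in a third-party application also installed on the mobile phone", that is, the phone handed to the intervention group.

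Section 3.12 opens with clinic BP and mean awake ABPM. It then frames the comparison of the main variables as before versus after app use. One paired t-test is assigned to BP values, weight, BMI, waist, urinary sodium and questionnaire score together. Chi-square and Kruskal-Wallis tests are mentioned for nonparametric variables, without saying which variables or which groups.

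**The concern.** A primary objective should tell the reader which result answers the trial's question. This one names eight measures of equal standing. It does not say whether one, some or all must favour the app, and the existence of Section 2.1 shows that primary status for all five items was chosen.

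The analysis section does not repair this. The objective asks about BP control and about app versus standard follow-up. The stated paired test concerns BP values and change within patients. A fall in mean BP from baseline could occur in both arms and would answer neither part of the objective.

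At stake is whether a reader of the results could tell which finding was the planned primary one, and whether that finding rests on the randomised comparison.

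**Working it through.** **Count of primary measures (Section 2).** (a) 2 + (b) 1 + (c) 2 + (d) 1 + (e) 2 = 8, or 7 if (a) is read as joint control.

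**When each is measured after baseline (Section 3.1).**

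| Measure | Post-baseline times |
|---|---|
| Office BP, weight, waist | visits 2, 3, 4, 5 |
| Awake ABPM | visits 2, 3, 5 |
| Adherence, dietary sodium, urinary sodium | 12 months only |
| Daily steps | none stated; capture described for the app phone only |

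Seven of the eight measures coincide at one visit only, visit 5. Steps are the exception: with no described control-arm capture, (d) cannot serve as a between-arm primary as written.

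**Objective against analysis.**

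| | Section 2 | Section 3.12 |
|---|---|---|
| Contrast | app vs standard follow-up | before vs after app use |
| BP quantity | control below thresholds | BP value |
| Order of measures | none | BP opens the section, then is listed with the others |

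**What the lack of a rule could mean for error.** The protocol gives no alpha, so there is no figure of its own to reproduce. Assume two-sided 0.05 per measure, between-arm tests at one visit, and any one measure counting as success.

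- Independent: 1 − 0.95^5 = 0.226; 1 − 0.95^8 = 0.337.
- Equicorrelated normal statistics, eight measures, by simulation: 0.250 at correlation 0.5; 0.157 at correlation 0.8.

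The range for eight measures is therefore about 16% to 34%. Several measures form natural pairs (office and ambulatory BP, dietary and urinary sodium, weight and waist), so the independent end is an upper bound rather than a best guess. These figures do not describe the paired test in Section 3.12.

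**What keeping all eight would cost.** With 50 per arm (Section 3.1), 80% power and no dropout, the detectable standardised difference is (z_(1−α/2) + z_0.80) × √(2/50).

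- α = 0.05: (1.960 + 0.842) × 0.2 = 0.56.
- α = 0.05/8 = 0.00625: (2.734 + 0.842) × 0.2 = 0.72.

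Power for a 0.5 SD effect falls from 71% to 41%.

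**What one binary primary can detect.** Take 20% control in the standard arm (assumed), 50 per arm, two-sided 0.05 and 80% power. With p̄ = (0.20 + 0.46)/2 = 0.33:

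n = [1.960 × √(2 × 0.33 × 0.67) + 0.842 × √(0.20 × 0.80 + 0.46 × 0.54)]² / 0.26² = (1.303 + 0.538)² / 0.0676 ≈ 50.

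So 46% in the app arm is detectable. The same formula gives about 33% if controls are at 10% and 68% if they are at 40%. Under Fisher's exact test, 20% against 46% has about 74% power rather than 80%.

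**The case against.** The document does lean one way. The hypothesis just before Section 2 names only adherence and BP control, and Section 3.12 opens with BP. Neither passage ranks the list, though. The same Section 3.12 then treats BP alongside weight, waist and the rest, and the primary heading still covers all five items.

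A reader might infer that the deciding visit is wide open, so that office BP, weight, waist and ABPM offer 4 + 4 + 4 + 3 = 15 candidate results. The documents do not support that. Section 3.1 sets a 12-month follow-up, gives the phone for 12 months and places the final visit at 12 months, and Section 3.12 compares before with after app use. Together these point to visit 5. The 15 results are scheduled measurements, not planned tests, and what remains is a missing label.

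A reader might also infer that one favourable parameter at any visit would count as success. The protocol states no such rule. If all parameters had to succeed, type I error would not inflate and the cost would fall on power. The fair criticism is that no rule is given.

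A multiplicity method may sit in an SAP that is not at hand, and its absence here is no finding. But this protocol itself fixes the primary set, and any SAP would inherit it. The chi-square test in Section 3.12 could be used to compare control rates between arms, but the text attaches it to neither.

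**Conclusion.** The point holds on the text: eight measures share primary status without ranking or success rule; no stated analysis compares BP control between arms; 12 months is implied but not labelled; and steps lack both an assessment time and described control-arm data. It should be corrected, and the correction is more than added detail, because the stated paired test does not answer the stated objective.

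The 16% to 34% family-wise error is conditional on an assumed 0.05 per measure and on an any-one-counts rule that the protocol does not contain. It shows why a rule is needed and is not this trial's error rate. Confidence is medium, since the cues towards BP and 12 months suggest that the authors may already intend something close to the proposed fix.

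**What to change.** In Section 2, name one primary outcome at visit 5 (12 months). One suitable choice is item (a), worded as the proportion controlled on both office BP (<140/90 mmHg) and awake ambulatory BP (<135/85 mmHg). Eligibility covers patients "who present clinic BP ≥ 140 and/or 90 mmHg, and wakefulness BP in ambulatory BP monitoring" at or above 135/85 mmHg, so joint control is 0% at selection in both arms. Move the remaining items to secondary and call earlier visits supportive. In Section 3.12, state a between-arm comparison of that outcome.

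Which outcome leads is the sponsor's choice. If two are kept, for example (a) and (b) at 12 months, either split alpha by Bonferroni (0.025 each) or use Holm's step-down procedure.

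The cost is wording in two sections. Visit 5 already collects office BP, ABPM and the adherence questionnaire, so no new measurement is needed. The downsides are that (b) to (e) lose primary status, and that a proportion is coarser than mean BP, with the detectable contrast shown above. At 0.025 each, the detectable app-arm rate against 20% in controls rises from 46% to 49%. Keeping (d) as a primary would need a step count in the control arm, which the protocol does not now describe.

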2.1. Secondary objective

- a) To evaluate the effects of the use of the monitoring application on: quality of life of patients with uncontrolled hypertension through WHOQOL questionnaire; sleep quality assessed by the Pittsburg questionnaire; anxiety level assessed by the HADS questionnaire; food consumption assessed by consumption questionnaires and food recall:
- b) Assess the ability of patients with uncontrolled hypertension to use the application

3. Methodology

3.1. Study design

Randomized study with patients with uncontrolled hypertension followed at the Outpatient Clinic of the Hypertension Unit of the Heart Institute (InCor-HCFMUSP), for the use of an application for monitoring and engagement to antihypertensive treatment - compared to the standard follow-up of the institution in a 12-month follow-up.

The study involves the direct participation of an institutional multidisciplinary team with an international partnership and a national institution of advanced technology in artificial intelligence. The hospital's team includes physicians, nurses, nutritionists, psychologists, physical educators and biomedical, supported by the institution's own innovation team. The international team includes all members of the Inavya Ventures LTd.

Will be included 100 patients diagnosed with primary arterial hypertension under drug treatment, with at least 3 classes of antihypertensive drugs in an optimized dose, aged 20 to 65 years, and who present clinic BP ≥ 140 and/or 90 mmHg, and wakefulness BP in ambulatory BP monitoring $\geq 135/85$ mmHg. Patients or their caregivers should also be able to use mobile phones and apps.

Patients with stroke sequelae or those with significant cognitive dysfunction will be excluded.

Randomization will be done in the 1:1 form using electronic randomization system, without knowledge by the team involved in the study. There will be two groups in the project,

so that, patients will be randomized to intervention group (application use) or control group (standard follow-up of the institution).

In the intervention group (N= 50), patients will receive a cellular device (by donation consigned by a telephone company) for the exclusive use of the application within 12 months. In this mobile device will be installed, with the guidance of the multidisciplinary team, the AVATR application developed in partnership with the company Inavya Ventures Ltd., where they will be digitized with individualized code for each patient, personal data, including age, gender, behavioral patterns and lifestyle habits (walks, type of diet, quality of sleep, etc.), and daily medications used.

The data will be allocated in a dedicated cloud and protected by cutting edge encryption. All this part of data capture and storage is in accordance with the rules of the General Data Protection Law (GDPL) as well as the General Data Protection Regulation (GDPR), the uk regulation.

Patients will have a 15 days adaptation period to the use of the application, where they will receive virtual guidance by the multidisciplinary team for the correct use. After this period, patients will perform an evaluation by the medical and nursing staff, where clinical data (clinic blood pressure, weight, height and abdominal circumference) will be collected and patients will answer questionnaires on quality of life, anxiety, sleep quality, food intake and therapeutic adherence. In this same consultation, patients will receive an automatic blood pressure measurement device (described in the methods) to make household blood pressure measurement according to nursing guidance. Blood samples will also be collected for biochemical profile (total cholesterol and fractions, triglycerides, fasting glycemia, potassium, serum creatinine) and 24-hour urine sample for urinary sodium dosage, these tests will be collected at the Research Center and the analysis will be performed by the institute's laboratory.

The application automatically receives input data from each patient, such as BP MEASUREMENTS by the device and also the steps walked recorded by own in a third-party application also installed on the mobile phone. This data is safely transferred to the cloud server and analyzed based on an algorithm developed with the help of healthcare professionals to generate a customized lifestyle modification program designed for each patient. The application has automatic messages for the time of medication, in addition to strengthening nutritional guidance, physical activity and emotional order through automatic motivating phrases and also by access to educational videos. Another important tool is speech recognition that allows the patient to send data by voice system when there is difficulty in typing communication.

The multiprofessional team will receive alerts by email or the application platform, according to pre-established limits of blood pressure or symptoms, allowing immediate contact of the team for the necessary guidance. The multidisciplinary team will contact patients in the digital intervention group every 4 weeks for guidance based on the insertions made by patients in the application during the period. The correct use of medication as well as the adoption of healthy life habits will be reinforced in this contact.

The control group (N= 50) will perform the same initial evaluation and answer the same questionnaires as described above for the intervention group. In this evaluation will receive guidance regarding the adoption of life habits by the multidisciplinary team. The control group will receive reinforcement of guidance only in clinic face-to-face visits.

The visits of the study after the patient's inclusion will take place every 12 weeks (Visits 2, 3, 4 and 5), totaling 4 visits after the initial visit, with the final visit after 12 months. Patients will perform 24-hour ambulatory blood pressure monitoring (ABPM) at visits 2, 3 and 5. In visits 2 to 5, the patient will have the measurement of blood pressure from the office, weight and abdominal circumference, and data on symptoms and events that occurred (hospitalizations, emergency room visits, symptoms) will be collected. In the last visit (12-month), in addition to these measures, the questionnaires performed on the first visit and laboratory dosages will be repeated.

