3.12. Statistical analysis

All analyses will be performed based on the complete population of the set of analyses, and all values of the clinic BP and the mean wakefulness of the ABPM will be included. The

characteristics of the patient at the initial visit will be described using mean \pm standard deviation or median deviation (quartiles) for continuous variables, or number (proportion in %) for categorical variables. To compare the main variables before and after using the application, the appropriate tests will be performed according to the type of the variable, that is, whether quantitative or qualitative. Thus, to compare the quantitative variables (blood pressure value, weight, body mass index, abdominal circumference, 24-hour urine sodium and questionnaire score), a comparative analysis of a paired t-test will be performed. For the nonparametric variables, the chi-square and kruskall wallis test will be used to compare them.

4. Expected results

The use of the artificial intelligence application for distance monitoring of patients with uncontrolled hypertension should provide greater engagement of patients and their families in treatment, and thus may lead to better blood pressure control, greater adhering to healthy lifestyle habits (decreased sodium intake, increased physical activity and improved quality of life) when compared to the follow-up currently performed at the institution. Better blood pressure control of these patients, who generally require a high number of medications, may consequently reduce the risks of complications and also the search for emergency services, which can harm the patient, and also encumber the health service. In addition, the integrated participation of a multidisciplinary team more actively ensures greater involvement with patient care, without the need for frequent returns to the Unit for better blood pressure control.

5. Timeline

Month	Activity
1st to 2nd month	Selection of participants
2nd to 3rd month	Signature of the GDPL and training of patients with application
5th to 6th month	Consultation for data collection and delivery of the blood pressure measurement device
7th to 12th month	Monitoring patients by staff through the application
7th to 12th month	Consultation for data collection and delivery of the blood pressure measurement device

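### In the application arm, weight, waist, questionnaires, bloods and urinary sodium are first measured after 15 days with the application, so the planned before-and-after test has no value from before use

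*Protocol*

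**What the plan says.** Protocol section 3.1 gives the order of events. First, "patients will be randomized to intervention group (application use) or control group". The intervention arm then receives a phone on which the application is installed. Next, "Patients will have a 15 days adaptation period to the use of the application", with virtual guidance from the team. The first described assessment follows: "After this period, patients will perform an evaluation by the medical and nursing staff, where clinical data" (clinic blood pressure, weight, height, waist) are collected. The questionnaires on quality of life, anxiety, sleep, food intake and adherence are answered at that point, and blood and 24-hour urine collection is described with the same evaluation.

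The control group "will perform the same initial evaluation and answer the same questionnaires as described above for the intervention group". At 12 months, "the questionnaires performed on the first visit and laboratory dosages will be repeated". Weight and waist are also taken at visits 2 to 5; the questionnaires and laboratory tests are described only at the first visit and at the last.

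Section 3.12 plans the analysis: "To compare the main variables before and after using the application, the appropriate tests will be performed". The quantitative variables it assigns to a paired t-test include weight, waist, 24-hour urinary sodium and questionnaire score.

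**The concern.** A paired test of before against after use needs a measurement from before use. In the order given, the first value of these outcomes in the application arm comes after randomisation and after 15 days with the application. In the control arm the same evaluation follows no such exposure. The baseline is therefore exposed to the intervention in one arm only.

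Adherence, sodium, body weight and abdominal circumference are all named under the primary objective (section 2, items b, c and e). For the questionnaires and laboratory tests there are only two time points, so no other visit can stand in for an affected first value. An analysis plan cannot repair this later, because it cannot recover a measurement that was not taken.

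**Working it through.** **Is a value from before use described anywhere?**

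| Measure | Before use | After 15 days | Later |
|---|---|---|---|
| Clinic BP | yes, for eligibility (3.1) | yes | visits 2 to 5 |
| Awake ambulatory BP | yes, for eligibility (3.1) | not listed | visits 2, 3, 5 |
| Weight, waist | none described | yes | visits 2 to 5 |
| Questionnaires | none described | yes | 12 months |
| Bloods, 24-hour urinary sodium | none described | yes | 12 months |

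The personal and lifestyle data entered at installation (section 3.1) are not these instruments or tests.

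**Which period do the first values reflect?** The previous-day dietary recall and the 24-hour urine cover 1 day, and the food-marker form covers 7 days (section 3.8). All of these lie inside the 15 days. The sleep questionnaire covers one month (section 3.10), so about 15/30 = half of it lies inside. Sections 3.9 and 3.11 give no window for the adherence scale or the anxiety scale.

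**What does an early shift do?** Let D be the true difference between arms at 12 months, c the change that both arms would show without the application, and s the shift already present in the application arm at the first visit.

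- Paired change, application arm: c + D − s
- Difference between arms in change: (c + D − s) − c = D − s
- Unadjusted difference between arms at 12 months: D
- Difference adjusted for baseline with slope b: D − b·s

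If the early shift is a lasting share f of the effect, then s = f·D. The difference in change is (1 − f)·D, and the adjusted difference is (1 − b·f)·D.

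The protocol gives neither f nor b. The only figure from stated times is 15/365 = 0.041, about 4%, and reading that as f assumes that the effect builds up linearly. The other values of f, and b = 0.5, are for illustration.

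| f (assumed) | Share of D kept, change (1 − f) | Share kept, adjusted (1 − 0.5f) | Share kept, unadjusted 12-month values |
|---|---|---|---|
| 0.041 | 0.96 | 0.98 | 1 |
| 0.10 | 0.90 | 0.95 | 1 |
| 0.25 | 0.75 | 0.875 | 1 |
| 0.50 | 0.50 | 0.75 | 1 |

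If the early shift is transient, s need not have the sign of D. A temporary worsening of self-reported scores makes D − s larger than D in size; a temporary improvement makes it smaller.

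**The case against.** The strongest reply is that exposure in those 15 days may be light. The protocol describes the period as guidance on correct use. The home blood pressure and glucose devices are handed over only at the evaluation (sections 3.1, 3.5, 3.6), so feedback based on them is not yet running. The team's reinforcing contact is every 4 weeks, so on that schedule none need fall within 15 days. This stands: contamination of the baseline is possible, not shown. But the protocol does not say whether medication reminders, lifestyle messages and videos are off during adaptation, and these address the outcomes being measured.

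A second reply is that the analysis plan, which is not at hand, may compare 12-month values between arms without adjustment. That comparison would be unaffected. It is not the paired test that section 3.12 sets for these variables.

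Three stronger readings are tempting, and the document does not support them.

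- **Exposure of months rather than 15 days.** Section 5 puts "Signature of the GDPL and training of patients with application" in months 2 to 3 and "Consultation for data collection and delivery of the blood pressure measurement device" in months 5 to 6. A reader might infer that each patient uses the application for several months before the first evaluation. But the table is a project calendar that opens with the selection of participants, and a note after it says that it is still to be validated. It fixes no individual patient's interval; the only per-patient figure is 15 days.
- **A large bias.** A reader might assume that the effect comes quickly and arrive at a sizeable loss. The protocol gives nothing on the speed of the effect, so any such figure reflects only the curve chosen.
- **A bias that always runs towards no effect.** That needs an early and persistent benefit. Starting an application can also shift self-reports temporarily, in either direction.

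**Conclusion.** The point holds as a defect in the order of assessments. For weight, waist, the questionnaires, bloods and 24-hour urinary sodium, no value from before use is described in the application arm. For those of them that section 3.12 lists for the paired test, the comparison it names cannot be made as worded. Any effect in the first 15 days is absorbed into the baseline of one arm. It is removed from the paired change and from any comparison of change between arms, and partly removed under baseline adjustment.

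The size is unknown. It could be small: about 4% of the effect if build-up is linear and the application is fully active from installation. Blood pressure lies outside the point because eligibility values exist from before use. The conclusion rests on reading section 3.1 in the order in which it is written, and on no earlier assessment being planned elsewhere.

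**What to change.** Take weight, waist, all questionnaires, bloods and the 24-hour urine in both arms before randomisation, or at the latest before the application is installed, and designate these values as baseline. Keep the day-15 contact for checking correct use and handing over the home devices. Use *initial visit*, *first visit* and *before* for the same time point throughout sections 3.1 and 3.12.

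No new measurement is needed. The cost is rescheduling the first assessment for up to 100 patients, and possibly one extra contact or a short delay in installation for the 50 patients in the application arm.

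As a separate housekeeping matter, reconcile the provisional calendar in section 5 with the 15-day period in section 3.1.
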